## COVID 19 Effects on Quality of Life

materials for analysis. Codes will be generated via the software and used to assist investigators in developing thematic material. Team members will confer and reach consensus on the results (peer debriefing). Iteratively, the meaning of the content will be derived and prepared for reporting. The de-identified transcripts and data will be subjected to auditing by an outside auditor with expertise in qualitative research methods. All media: paper and electronic will be held in secure offices within locked metal filing cabinets. Electronic media will have further security using devices meeting federal standards for encryption and password protection.

Quantitative analysis will be analyzed by [name] with assistance from a graduate student employee using SPSS.

## **12. Provisions to Monitor the Data to Ensure the Safety of Subjects**

The study is not expected to involve more than minimal risk to participants. Some people may experience sadness depending on the effect of COVID on their lives and changes or losses encountered.

## **13. Withdrawal of Subjects**

Participants will be free to withdraw from the study at any point. However, any previously collected data will remain for use in the study up to the point of termination from the study. Withdrawal should be in writing, although it may be anticipated that some participants may terminate orally. Investigators will respect the autonomy of participants and record the oral termination. Reasons for participants to terminate from the study could include several precipitating events: change in residence, change in health status, inconvenience, timing, or other subjective or objective factors. Reasons for investigators terminating participants from the study might include abusive behavior of participants, unable to contact the participant for follow-up, or potential cognitive change of participant that might impair ability to consent. The ability and conditions of withdrawal will be stated clearly in the consent document.

## **14. Data Management/Confidentiality**

The members of the research team having access to the data include the investigators (PI, Co-PIs, graduate student investigators added to the project who have completed HIPAA and CITI training). Once all data collection is completed, the only team member requiring access to the identifiable data will be the PI and Co-PIs. The research will not require disclosing any protected information. The research team does not anticipate receiving any information that requires additional protections (i.e. HIV status, etc.). Because the research is being conducted using NIH funding and is registered in clinicaltrials.gov, a Certificate of Confidentiality will be used to protect the data from forced release. Although the risk of exposure of identifiable information is remote, a participants identify might be deduced depending on the nature of disclosures they make during the interview and the geographic region they reside.

## COVID 19 Effects on Quality of Life

Extreme care will be taken to protect the data using UNM HSC IT recommended technology for encryption and password protection. The team will purchase a portable storage device (jump drive) for that purpose. Only the PI and Co-PIs will have physical control of storage devices. Identifiers will be held separately from the storage device, in the PIs secure office, in a secure and locked metal filing cabinet. Each participant will be given a unique code for data analysis purposes. In every instance, identifiable information is secured separately from the data and participant code. Identifying data will be held for three years, per IRB recommendation, and thereafter destroyed using a secure shredding bin. The identifying data includes the audio recordings of participants. De-identified data will be kept indefinitely for manuscript purposes. Data will not be transferred electronically and work with the data will occur on non-networked computers owned by the division. No identifiable health information is being collected.

## 15.Data and Specimen Banking

N/A

## 16.Risks to Subjects

The investigators anticipate minimal risk to subjects being surveyed and interviewed for the study. However, due to the severity and extent of the COVID-19 health emergency, they do anticipate some participants may express extreme stress, depression, or anxiety. The investigators will have a readily available and sharable list of mental health resources, financial resources, and food bank resources to mitigate distress caused by the emergency. Reversibility of risks depends on the length of the health emergency and improvement in socio-economic status for some participants. These may be outside the direct influence of investigators, but efforts to mitigate will be offered through providing reliable information and referral. Through careful handling of data, as described above, investigators will minimize the risk of breach of confidentiality and/or privacy. The risks will be described in the consent.

Since participants will be giving individual interviews, it is not likely the procedures will put non-participants at risk. However, if participants disclose being victims of domestic violence or perpetrating domestic violence or performing acts of abuse or neglect of children or elderly co-habitants, it is necessary in the consent to give warning that as health professionals, the investigators would be bound to report such disclosures per state law.

## 17.Potential Benefits to Subjects

No direct benefits are expected to accrue to research participants.

## 18.Recruitment Methods Where I left off:

All recruitment material(s) (e.g., advertisement, flyer, e-mail, letter, phone script, etc.) to be used in the study must be submitted with this exemption request.

## COVID 19 Effects on Quality of Life

This is a prospective study. Research will be conducted via telephonic or wireless technologies enabling individual contact with prospective participants. Researchers will be based in HSC offices or, from work at home locations as determined by the HSC as necessary due to the pandemic. Prospective participants will be reached via public directories available across every New Mexico county and a random pattern will be used to systematically use the directory listings. There will also be opportunities for participants to elect to contact the researchers in order to be surveyed, by placing print notifications via public service announcements to rural and urban news organizations or via advertisement. Respondents will also have the option of writing their responses and returning by mail.

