### Specific Aims:

Aim 1: Extensively evaluate the perceived quality of life (QOL) of urban vs. rural living people during the COVID-19 emergency, thereby assessing similarities and differences in QOL impact during the national health emergency.

Aim 2: Evaluate the daily lived experience of people living in rural and urban areas during the health emergency in regard to biopsychosocial factors impacting the well-being of individuals and families, including access to services and resources for health, finances, technology, news and information use, use of time, and psychosocial support.

Aim 3: Determining use of resilience strategies (protective factors) of urban vs. rural living people during the national health emergency.

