### **4. Inclusion and Exclusion Criteria**

Inclusion Criteria: Adult residents of New Mexico of any gender, gender identity, and ethnic origin speaking the English language, living in rural or urban/suburban locations, ages 18-85, will be eligible to participate in the study. Screening for eligibility will occur at time of making contact. Pregnant women are not excluded from participation because this special status is not relevant, the research poses less than minimal risk, and pregnancy is not the focus of the study.

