## COVID 19 Effects on Quality of Life

Exclusion: Incarcerated individuals, children, and those with inability to give consent will be excluded from the study. Assessing the capacity of consent of the person is limited due to the method of surveying by telephone or internet. The investigators will endeavor to ensure ability to consent by questioning the potential subject about their understanding of the research, their understanding of the right to consent or withdraw (i.e. understanding choice), their ability to reason, clarity in decision-making, and noticing confusion by the potential participant, or noticing cues of impairment (i.e. difficulty with orienting to temporal events, days, months). Investigators will be familiar with principles of competency for consent including items from the MacArthur Competency Assessment Tool for Clinical Research (MacCAT-CR).

Residents of New Mexico may be excluded if they are unable to speak English since the WHOQOL-BREF may not be available in other languages of the resident. The researchers will be preparing for future research using Spanish translations, but will not be modifying the protocol at this time in order to be timely in gathering the urgent data.

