## 10. Study Procedures

Contact information for accessible prospective participants will be derived from publicly available directories for the 33 counties of New Mexico. The research team will be attempting to obtain a representative sample of all New Mexico residents using proportional systematic sampling with a random start point, and a sampling interval of 10, to make contact via telephonic or internet technologies. The goal is to obtain a probability sample for residents by age, gender, ethnicity, and geographic distribution into two cohorts: urban and rural residents. It is desirable to generate a sample that closely mirrors the population of New Mexico.

Researchers making contact will use a contact script to introduce themselves, the purpose of the research, and determine the interest of the person in participating. If a person is

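### Volunteers are admitted alongside a systematic directory sample, so the combined sample cannot be the probability sample the protocol sets as its goal, and no analysis by entry route is described

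*Protocol*

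**What the plan says.** **Sampling goal.** Protocol section 10 (Study Procedures) describes the team as "attempting to obtain a representative sample of all New Mexico residents using proportional systematic sampling with a random start point", with a sampling interval of 10. It continues: "The goal is to obtain a probability sample for residents by age, gender, ethnicity, and geographic distribution into two cohorts: urban and rural residents".

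**Second route.** Protocol section 18 (Recruitment Methods) repeats the directory route and then adds: "There will also be opportunities for participants to elect to contact the researchers in order to be surveyed". These people are to be reached "by placing print notifications via public service announcements to rural and urban news organizations or via advertisement". The same section says: "Respondents will also have the option of writing their responses and returning by mail". Section 10 otherwise has the questionnaire items read to the participant.

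**Eligibility.** Section 4 limits entry to adults "speaking the English language, living in rural or urban/suburban locations, ages 18-85, will be eligible to participate in the study", and adds that "Residents of New Mexico may be excluded if they are unable to speak English". Section 28 rules out recruitment on tribal nations, while leaving Native individuals free to take part.

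**Target and analysis.** Number of Subjects gives up to 300 participants, 150 per cohort, and a power of 0.8, with no cap or sub-target by source. Section 10 lists the demographic items; entry route and response mode are not among them, and the intake form it points to is not in the documents. For the quantitative analysis, Protocol section 11 names who will do it and the software, and the SAP's Quantitative paragraph names who did it. Neither describes any use of route or mode.

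**The concern.** A probability sample needs a known, non-zero selection probability for each member of the sampled population. Systematic selection from a list can supply that for listed people. Answering an announcement cannot.

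Two things are at stake:

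- **Description of the sample.** If both routes fill the same 150 per cohort, the combined sample lacks the property that section 10 seeks, however few volunteers there are.
- **The Aim 1 comparison.** Aim 1 is to "Extensively evaluate the perceived quality of life (QOL) of urban vs. rural living people during the COVID-19 emergency". People who come forward may score differently on the WHOQOL-BREF from people reached through a directory. If volunteering is more common in one cohort, or goes with a different score shift there, part of the observed rural-urban difference would reflect route of entry. No planned analysis would show this.

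**Working it through.** **1. The sampling claim (no arithmetic needed).** Section 10 gives one route with a defined selection rule. Section 18 gives a second with none. Number of Subjects counts both towards 150 per cohort, and neither analysis section separates them. The union of a systematic sample and self-selected volunteers is not a probability sample. The directory part alone could be one, for listed and eligible residents, subject to non-response.

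**2. The plan's own figure.** The stated power of 0.8 cannot be reproduced, because no effect size, SD, significance level or sidedness is given. Assuming a two-sided 5% test and unit SD:

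- SE of the contrast = √(1/150 + 1/150) = √(2/150) = 0.1155 SD
- Detectable difference at 80% power = (1.960 + 0.842) × 0.1155 = 0.323 SD

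This back-solved value serves only as a benchmark.

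**3. Possible bias in the contrast.** Let f be the volunteer share and g the score shift that goes with volunteering, in SD units. Then

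bias = f(rural) × g(rural) − f(urban) × g(urban)

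With no true difference, the rejection rate is 1 − Φ(1.96 − bias/0.1155) + Φ(−1.96 − bias/0.1155). All shares and shifts below are assumptions.

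| Case | Bias (SD) | Rejection |
|---|---|---|
| Equal shares, equal shifts | 0 | 5% |
| Share gap 10 points, shift 0.3 | 0.10 × 0.3 = 0.03 | 6% |
| Equal 30% shares, shifts 0.5 and 0.2 | 0.15 − 0.06 = 0.09 | 12% |
| Share gap 20 points, shift 0.5 | 0.20 × 0.5 = 0.10 | 14% |
| Share gap 30 points, shift 0.5 (extreme) | 0.30 × 0.5 = 0.15 | 26% |

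**4. What each analysis removes.** A route main effect brings the share-gap cases back to 0, because the shift is common to both cohorts. It does not help when shifts differ. With equal 30% shares it averages the two within-route contrasts: 0.7 × 0 + 0.3 × (0.5 − 0.2) = 0.09 SD, unchanged. Restricting to directory participants gives 0 in every case. So does the directory contrast from a model with a route-by-cohort term.

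**5. Cost of the directory-only analysis at d = 0.323.** Power = Φ(0.323/SE − 1.96), for assumed rural/urban volunteer shares:

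- 30/20%: n = 105 + 120, SE = √(1/105 + 1/120) = 0.1336, power about 68%
- 40/20%: n = 90 + 120, SE = 0.1394, power about 64%
- 50/20%: n = 75 + 120, SE = 0.1472, power about 59%

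**The case against.** **The commitment is soft.** The probability sample is a goal, the representative sample is something attempted, and section 3 calls the research exploratory. The aims and hypothesis are rural-urban contrasts, and no passage plans a statewide estimate. This stands. A reader might infer that such an estimate is planned and would be invalid; the documents do not say so. What remains is that section 18 makes the goal in section 10 unattainable for the combined sample by design.

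**Pooling is not stated.** Also true. It is inferred from the single target per cohort and from the absence of any separation by route. The documents offer no other reading, but it is still an inference.

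**Volunteers are not the only obstacle.** English-only eligibility, the age range, directory listing, non-response and the tribal-nations limit all narrow coverage. Two equal cohorts of 150 would mirror the state only after weighting, unless the population happens to split equally. This stands: removing volunteers would not by itself yield a sample of all residents.

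**Bias in Aim 1 is speculative.** It is tempting to conclude that the contrast is biased. The documents do not support that. They give neither volunteer shares nor shifts, and notices go to both rural and urban outlets. That does not establish equal shares, but nothing points to a gap.

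**Route may be recorded.** The intake form is not available, so this cannot be ruled out. Even so, no use of route in analysis is described.

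**Response mode.** A reader might also want the main comparison adjusted for mail reply. That is unsafe. Section 18 makes mail an option respondents choose, so the choice may depend on quality of life, and adjustment could then distort a true difference. It is also unclear whether the option is for everyone or only for volunteers.

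**Conclusion.** The point holds as a conflict between sections 10 and 18. The combined sample cannot be a probability sample of all New Mexico residents. This follows from the definition once both routes count towards one target, and needs no assumption about effect size.

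The effect on Aim 1 is conditional and its size unknown. On assumed inputs it runs from 0 to 0.10 SD, with false rejection of 5% to 14%, or 0.15 SD and 26% in an extreme case. These figures assume 150 per cohort, unit SD and a two-sided 5% test. They show what could happen and are not evidence that it did. Confidence is high for the wording conflict and does not extend to the bias. The plan should be corrected, but the rural-urban comparison is not shown to be invalid.

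**What to change.** 1. **Reconcile sections 10 and 18.** Drop the probability-sample and all-residents wording for the combined sample. Describe it as English-speaking New Mexico residents aged 18 to 85 reached through directories or volunteering, with no recruitment on tribal nations (section 28).
2. **Record entry route** (directory or volunteer) for every participant. The SAP is written in the past tense, so collection may be over. In that case recover route from contact records and recordings while they are held; section 14 has identifying data, including audio, destroyed after three years.
3. **Report the Aim 1 contrast in directory participants alone**, or from a model with a route-by-cohort term, as a sensitivity analysis beside the full-sample result. Prespecify it if still possible; otherwise label it post hoc. A route main effect alone is enough only if the volunteer shift is the same in both cohorts.
4. **Clarify who may reply by mail and record response mode**, but use mode only in a sensitivity analysis.

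The cost is two data fields or a retrospective check of records, one extra analysis, and revised wording. The downsides are a narrower population statement and the lower directory-only power shown above, which is why that result sits beside the full-sample one and does not replace it. The directory-only analysis would also leave out any tribal-nation residents who entered by volunteering. If route cannot be recovered, the wording correction is still feasible and still needed.

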## 19. Provisions to Protect the Privacy Interests of Subjects

Data will be collected, maintained, and archived or destroyed per HSC Data Security Best Practices, including:

1. **Best Practice for data collection** is for it to be directly entered onto a data collection form that is in a secured access folder on an HS drive behind a firewall, or in a secure UNM Data Security approved system such as RedCap.
2. **Data collection of de-identified data**, if done in a clinical setting or other setting that does not allow direct entry into a secured system, may be done temporarily using a personal or university owned electronic storage device or hard copy document. **The important security safeguard is that no identifiers be included if the data is entered or stored using an untrusted device or storage.**
3. **Permanent (during data analysis, after study closure)** storage must reside on HSC central IT managed storage. Processing of data (aggregation, etc.) are to be carried out in such a way as to avoid creating/retaining files on untrusted storage devices/computers. Trusted devices are HSC managed and provide one or more of following safeguards: access logs, encryption keys, backups, business continuity and disaster recovery capabilities.
4. **Alternate storage media** must be approved by HSC IT Security as meeting or exceeding HSC central IT provided security safeguards.

Our process is to immediately de-identify data collected so that privacy is maintained.

## 20. Economic Burden to Subjects

N/A

## 21. Compensation

NONE

## 22. Consent Process

## **23. Documentation of Consent**

There will be an IRB approved consent process. Participants **MUST** be provided study information to include a disclosure that the activities involve research, a description of the research procedures, a disclosure that participation is voluntary and the name and contact of information of the PI. This can be in the form of a letter, email, verbal script or information sheet. Consenting will take place with members of the approved research team: [name], [name], and [name], and graduate student researcher [name].

## **24. Study Test Results/Incidental Findings**

Study results will be aggregated data and thematic data.

## **25. Sharing Study Progress or Results with Subjects**

The researchers intend to share the findings by submitting to journals. Participants can elect to opt in to receive research results.

## **26. Inclusion of Vulnerable Populations**

Screening for eligibility will occur at time of making contact. Pregnant women are not excluded from participation because this special status is not relevant, the research poses less than minimal risk, and pregnancy is not the focus of the study. Exclusion: Incarcerated individuals, children, and those with inability to give consent will be excluded from the study.

## **27. Community-Based Participatory Research**

N/A

## **28. Research Involving American Indian/Native Populations**

Native American/American Indian subjects are not the key focus of this research, and recruitment will not occur on any tribal nations, but American Indian/Native Population individuals may elect to participate in the research.

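### The protocol aims at a probability sample of all New Mexico residents but bars recruitment on tribal nations, and neither document reconciles the two or limits the conclusions accordingly

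*Protocol*

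**What the plan says.** **Target.** Protocol Section 10 (Study Procedures) has the team "attempting to obtain a representative sample of all New Mexico residents using proportional systematic sampling", with a random start and an interval of 10. It continues: "The goal is to obtain a probability sample for residents by age, gender, ethnicity, and geographic distribution into two cohorts: urban and rural residents". It adds: "It is desirable to generate a sample that closely mirrors the population of New Mexico". Later in the same section, focus-group members are described, without hedging, as reflecting the state on several characteristics, including geography and ethnicity.

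**Frame.** Contacts come from public directories for the 33 counties (Section 10). Section 18 (Recruitment Methods) says: "Prospective participants will be reached via public directories available across every New Mexico county". Neither section sets tribal land aside. Section 18 also lets people contact the team in response to notices or advertisements.

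**Restriction.** Section 28 says "recruitment will not occur on any tribal nations", and in the same sentence that "American Indian/Native Population individuals may elect to participate in the research".

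**Eligibility.** Section 4 admits English-speaking adult residents aged 18-85 of any ethnic origin. Living on tribal land is not an exclusion. On language it says: "Residents of New Mexico may be excluded if they are unable to speak English".

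**Analysis.** Protocol Section 11 and the SAP name who analyses the questionnaire. Neither mentions weighting, coverage, recruitment route or the population to which results apply.

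**The concern.** The population the study sets out to describe is wider than the one its recruitment rule lets it sample. The hypothesis and all three aims concern rural and urban people, and Section 2 intends the findings to inform rural and urban stakeholders and those in governance. Without a stated limit, results would be read as applying to communities where the team had decided not to recruit.

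There is also a practical gap. A caller working through a county directory at every tenth listing has no instruction for a listing on tribal land. It could be called, skipped and replaced, or removed beforehand. Different callers could do different things, and the selection probabilities could not then be reconstructed.

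**Working it through.** **1. The plan's own figure.** The only relevant number is power of 0.8 with 150 per group (Number of Subjects). It cannot be reproduced, because significance level, sidedness, effect size and SD are not given. Assuming two-sided 0.05, it corresponds to a difference of (1.960 + 0.842) × √(2/150) = 0.32 SD. The power statement does not depend on the present point; 0.32 SD serves below only as a yardstick.

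**2. Can the design yield a probability sample of all residents?** That requires every member of the target population to have a known, non-zero chance of selection. By route of entry:

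| Route | Source | Chance of selection |
|---|---|---|
| Directory listing outside tribal nations | Section 10, random start, interval 10 | 1/10 per listing, if the interval is applied throughout |
| Directory listing on a tribal nation | Section 10 frame, barred by Section 28 | 0 if the bar covers calls; otherwise undefined |
| American Indian individual who elects to take part | Section 28 | Unknown |
| Self-referred after a notice or advertisement | Section 18 | Unknown |

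The second row breaks the requirement for residents of tribal nations. The third and fourth may bring some of them in, but with no known probability and so no valid design weight. Opting in also addresses ethnicity, whereas the bar is by place, and Section 10 names both dimensions.

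**3. Does it affect the rural-urban contrast?** Let w be the share of a cohort's population that is not covered, and g the mean of the covered part minus the mean of the uncovered part. The covered mean differs from the full mean by w × g, so

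bias in (rural − urban) = w_R × g_R − w_U × g_U.

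None of the four quantities is in the documents. Rural and urban are not defined, and tribal land is not assigned to either cohort. To see whether any figure could be defended, assume w_U = 0, nobody from tribal land taking part, w_R of 5-30% and a gap of 0.2-0.8 SD in absolute size:

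- 0.05 × 0.2 = 0.01 SD
- 0.10 × 0.5 = 0.05 SD
- 0.20 × 0.5 = 0.10 SD
- 0.30 × 0.8 = 0.24 SD

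The range is 24-fold (0.24/0.01), from negligible to three quarters of the yardstick (0.24/0.32 = 0.75). The sign follows that of g_R, which is unknown. These figures show that the assumptions settle the answer; they are not an estimate for this study.

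**The case against.** The strongest reply is that Section 28 is an openly disclosed, specific limit on the general frame in Section 10, in a study that calls itself exploratory, and that Section 10 speaks only of an attempt, a goal and something desirable. Much of this stands. A reader might infer that the protocol claims to have a representative sample; for the survey it does not. Only the focus-group sentence is unhedged. Still, a goal that the protocol's own rule makes unattainable needs correcting.

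A second reply is that contact is by telephone or internet, so Section 28 may bar only recruiting in person. The text allows this reading. But the protocol describes no in-person recruitment, so the restriction would then do almost nothing. The plan does not say which is meant, and callers need a rule either way.

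Three stronger readings are tempting and not supported:

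- **That American Indian people, or residents of tribal land, are excluded.** The bar is on where recruitment happens. Eligibility is open to any ethnic origin, and both opting in and self-referral are allowed. The segment is under-covered to an unknown degree, not shown to be lost.
- **That the rural-urban difference is over-stated.** No result is reported in either document, the placing of tribal land in the rural cohort is an inference, and the bias could shrink or enlarge the contrast.
- **That the English-only rule is part of the same fault.** It is a separate restriction, stated and explained in Section 4. It matters here only because the restated population should carry it.

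**Conclusion.** The conflict is real, and it concerns scope. With Section 28 observed as a limit on contact, the directory sample cannot be a probability sample of all New Mexico residents by ethnicity and geography, and the opt-in and self-referral routes do not make it one. This rests on the wording of Sections 10, 18 and 28 and needs no assumed figure.

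An effect on the rural-urban contrast is possible if tribal land lies mostly in the rural cohort. That is plausible but not stated, and neither size nor direction can be found from the documents. No bias figure should be attached to the study. The point is worth correcting because it changes which population the conclusions can be said to cover.

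**What to change.** 1. In Sections 1 and 10, restate the population sampled from directories, and to which conclusions apply, as English-speaking adults aged 18-85 living in New Mexico outside tribal nations. Remove the all-resident target ("attempting to obtain a representative sample of all New Mexico residents"), the mirroring sentence ("It is desirable to generate a sample that closely mirrors the population of New Mexico") and the matching focus-group wording.
2. State one rule for callers: listings whose address identifies them as on tribal land are removed before the sampling interval is applied. The documents do not say that every directory shows addresses, so the rule can apply only where one does.
3. Leave eligibility in Section 4 unchanged. A new exclusion for residents of tribal land could shut out people whom Sections 18 and 28 may admit.
4. Record route of entry, flag self-referred participants, and add to the SAP a repeat of the rural-urban comparison in directory-sampled participants alone.
5. Report the ethnic and county make-up of each cohort beside the state's, and state the limit on generalisation.

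**Cost:** protocol and SAP wording, one frame-cleaning step, one recorded variable and one further comparison, which will be less precise because it uses fewer people. No extra participants are needed. The main downside is a narrower stated scope.
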